7.2 Discontinuation from Study Treatment

7.2.1 Temporary Cessation of Dosing in an Individual Participant:

- Subjects with grade 3 GI-related AEs will pause dosing for up to 72 hours. Dosing may be restarted when/if symptoms improve, after discussion with the sponsor medical monitor. If symptoms do not improve within 72 hours then the subject will be withdrawn from the study.
- Subjects with non GI-related grade 3 adverse events, not attributed to Covid-19 infection, will pause dosing for up to 72 hours, unless the baseline value was grade 2. Dosing may be restarted when/if symptoms improve, on discussion with the sponsor medical monitor. If symptoms do not improve within 72 hours then the subject will be withdrawn from the study.

The participant should discontinue treatment permanently if the AE occurs a second time on restarting treatment.

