7.2.2 Permanent Cessation of Dosing in an Individual Participant

It may be necessary for a participant to permanently discontinue study treatment. If study drug is definitively discontinued, the participant will be encouraged by the investigator to continue to participate in all scheduled study visits and assessments, so that study data will be collected for the participant per protocol. Every effort should be made to keep participants in the study. Individual treatment stopping rules are:

- “Any CTCAE grade 4 gastrointestinal-related adverse event.”
- “Any non GI-related CTCAE grade 4 adverse event, not attributed to Covid-19 infection.”
- “A new diagnosis of HIV / AIDS”

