5.3.3.3 S/F Ratio

The S/F ratio will be calculated as:

$$\text{S/F ratio} = \text{SpO}_2 (\%) / \text{FiO}_2 (\text{fraction of 1}).$$

The S/F ratio will be expressed to 0 dp.

Missing S/F ratios will be imputed using the rules in [Table 5](#).

Table 5 Rules for Imputation of Missing S/F Ratios on Individual Study Days 1-14

Reason for Missingness	Data Availability	Value to be Imputed
Participant died	N/A	0
Participant was discharged	N/A	Last S/F ratio recorded prior to discharge
Participant withdrawn from the study	N/A	Not imputed, value will remain as missing.
Other reason	S/F ratio available within window of +/- 1 day	Average of non-missing S/F ratios reported on the day before and day after the study day with missing data
Other reason	No S/F ratio available within window of +/- 1 day	Not imputed, value will remain as missing.

Trough S/F ratio is defined as the lowest S/F ratio reported in Days 1-14. Participants who die on or before Day 14 will have their trough S/F ratio imputed to 0.

If more than one S/F ratio is provided for a relevant study day, the lowest S/F ratio reported for that study day will be used in all summaries and analyses.

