7.3 Missing Data

7.3.1 General

Participants who discontinue treatment before the end of the scheduled 14 days treatment period will remain in the study and complete assessments as scheduled unless they die, start an alternate experimental treatment, or withdraw consent. Data collected at scheduled visits following discontinuation of study treatment will be included in all analyses.

Participants who are discharged from hospital before the end of the 42-day study period will be asked to complete a participant diary everyday with details of their symptoms, any AEs experienced and any changes to their concomitant medications.

Imputation rules for individual variables with missing data have been provided in [Section 5.3](#).

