9.2 Primary Efficacy Analysis

9.2.1 Primary Efficacy Estimand

The primary estimand will be the effect of EDP1815 compared to placebo on the change from baseline to trough S/F ratio in Days 1-14.

The population summary measure of interest will be the difference in mean change from baseline in trough S/F between EDP1815 and placebo.

Intercurrent events will be accounted for in the following manner:

Table 9 Intercurrent Event Strategies for the Primary Estimand

Intercurrent event	Strategy to account for intercurrent event
Treatment discontinuation before the end of the 14-day treatment period	Treatment policy Trough S/F ratio will be taken as the lowest recorded value on or off treatment
Death prior to day 14	Composite Trough S/F ratio will be imputed as 0
Discharge prior to day 14	While-on-treatment Trough S/F ratio prior to discharge will be used. Participants will be assumed to remain above trough value after discharge.
Withdrawal from the study prior to day 14.	While-on-treatment Trough S/F ratio prior to starting study withdrawal will be used

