9.3 Secondary Efficacy Analyses

9.3.1 Change from Baseline in S/F Ratio

9.3.1.1 Estimands

The endpoints will be the change from baseline in S/F ratio as measured on Days 4, 7, 10 and 14. The population summary measure of interest will be the difference in mean change from baseline in S/F ratio between EDP1815 and placebo at the relevant study day.

The intercurrent event strategy for these estimands is described in [Table 10](#).

Table 10 Intercurrent Event Strategies for the Change from Baseline in S/F Ratio Secondary Estimands

Intercurrent event	Strategy to account for intercurrent event
Death prior to the study day of interest	Composite S/F ratio will be imputed as 0
Discharge prior to the study day of interest	Composite Last S/F ratio prior to discharge will be used. Participants will be assumed to remain above this value after discharge.
Treatment discontinuation before the study day of interest without withdrawal from the study	Treatment policy The actual S/F ratio reported at the timepoint will be used regardless of treatment discontinuation
Withdrawal from the study prior to the study day of interest.	While-on-treatment Participants will be excluded from the analysis at that study day

Data missing for reasons other than an intercurrent event will be imputed as defined in [Table 5](#).

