9.3.3 WHO OSCI Score

9.3.3.1 Estimands

The endpoints will be recorded (inpatients) or derived (outpatients) WHO OSCI score at Days 4, 7, 14, 21 and 42. Population summary methods will be:

- Percentage of participants at each level of the WHO OSCI score
- Percentage of participants with each possible shift from Baseline in WHO OSCI score
- Percentage of participants remaining at their baseline WHO OSCI score (or lower)

- Percentage of participants reporting each level of WHO OSCi score at their worst post-baseline day

The intercurrent event strategy for these estimands is described in [Table 11](#).

Table 11 Intercurrent Event Strategies for the WHO OSCi Score Secondary Estimands

Intercurrent event	Strategy to account for intercurrent event
Death prior to the study day of interest	Composite WHO OSCi score of 8 will be carried forward to all further study days
Discharge prior to the study day of interest	Treatment policy The WHO OSCi score will be derived from the participant daily diary using the rules in Section 5.3.3.4
Treatment discontinuation before the study day of interest and no other experimental treatment not considered standard of care initiated	Treatment policy WHO OSCi score used as recorded for inpatients or derived for outpatients from the participant daily diary using the rules in Section 5.3.3.4
Withdrawal from the study due to initiating other experimental treatment not considered standard of care before the study day of interest	While-on-treatment Participants will be excluded from the analysis at that study day

Data missing for reasons other than an intercurrent event as detailed above will not be imputed.

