9.3.4 Overall Survival and Intubation and Mechanical Ventilation Free Survival

9.3.4.1 Estimands

The endpoint will be time to event in days as defined in [Section 5.3.3.5](#). The population summary measure of interest will be the hazard ratio for the EDP1815 group compared to the placebo group.

The intercurrent event strategy for these estimands is described in [Table 12](#).

Table 12 Intercurrent Event Strategies for Overall Survival and Intubation and Mechanical Ventilation Free Survival Secondary Estimands

Intercurrent event	Strategy to account for intercurrent event
Discharge prior to Day 42	Treatment policy Participants actual status will be used
Treatment discontinuation before Day 14 without withdrawal from the study	Treatment policy Participants actual status will be used
Withdrawal from the study	While-on-treatment Participants will be censored at the time of withdrawal from the study.

For the interim analysis presented at the DMC meeting when 60 patients have completed 21 days in the study, subjects who are still ongoing and have not met the criteria for the relevant event will be censored at the date of the data cut.

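### An unimproved Grade 3 adverse event ends study participation, while a Grade 4 event ends dosing only, so outcome data are lost after an AE trigger

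*Protocol*

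**What the plan says.** Protocol 7.2.1 concerns temporary cessation of dosing and has two bullets: Grade 3 GI events, and Grade 3 non-GI events not attributed to COVID-19 (with an exemption where the baseline value was already Grade 2). Each allows a dosing pause of up to 72 hours and ends with the same sentence: "If symptoms do not improve within 72 hours then the subject will be withdrawn from the study". If the event recurs after restart, the section stops treatment permanently and does not mention leaving the study.

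Protocol 7.2.2 lists Grade 4 events as reasons to stop study drug for good. It adds that "the participant will be encouraged by the investigator to continue to participate in all scheduled study visits and assessments". Protocol 7.1 (item 3) likewise stops dosing on ICU admission but keeps the participant to Day 42 where practical. Sections 7.1 and 7.2.2 both ask sites to retain participants as far as they can.

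SAP 7.3.1 says: "Participants who discontinue treatment before the end of the scheduled 14 days treatment period will remain in the study and complete assessments as scheduled". Its stated exceptions are death, starting an alternate experimental treatment and withdrawal of consent. An unimproved Grade 3 event is not among them.

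**The concern.** The rule is ordered the wrong way round by severity: Grade 3 ends participation, Grade 4 ends only dosing. It also conflicts with the plan's own estimands, which handle treatment discontinuation by treatment policy and so need data after dosing stops.

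Study withdrawal has separate and less informative rules in the SAP. A participant who leaves under 7.2.1 is no longer observed daily, and the reason is an adverse event, so the missingness may be related to outcome. If such events were more frequent in one arm, the loss would be unequal. The documents do not show that this will happen, but the rule provides the route. The GI bullet has no exemption for events attributed to COVID-19, so GI illness from the infection itself can also trigger withdrawal.

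**Working it through.** **1. Consequence of each trigger (Protocol Section 7)**

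| Trigger | Dosing | Study follow-up |
|---|---|---|
| Grade 3 AE, not improved in 72 h (7.2.1) | stops | ends |
| Grade 3 AE, recurs on restart (7.2.1) | stops | no withdrawal stated |
| Grade 4 AE (7.2.2) | stops | continues (encouraged) |
| ICU admission (7.1, item 3) | stops | continues to Day 42 where practical |

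Only the first row ends follow-up.

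**2. What the SAP then does with the participant**

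| Endpoint | Treatment stopped, still in study | Withdrawn from study |
|---|---|---|
| Trough S/F (Table 9) | lowest value on or off treatment | "Trough S/F ratio prior to starting study withdrawal will be used" |
| By-day S/F (Tables 5, 10) | actual value | "Not imputed, value will remain as missing"; "Participants will be excluded from the analysis at that study day" |
| WHO OSCI (Table 11) | recorded or diary-derived score | withdrawal row covers only starting another experimental treatment; otherwise "Data missing for reasons other than an intercurrent event as detailed above will not be imputed" |
| Overall and ventilation-free survival (Table 12) | actual status | "Participants will be censored at the time of withdrawal from the study" |
| Discharge, SpO2, recovery (Table 13) | actual values | censored at withdrawal |

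**3. Direction for the primary endpoint.** If withdrawal is on day w < 14, the trough is the minimum over Days 1 to w. A minimum over a shorter window is equal to or greater than the minimum over Days 1–14, so the recorded trough can only equal or exceed the true one. A later death by Day 14 may also go uncaptured and so not be scored 0.

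**4. The plan's precision figure.** Protocol Table 4 and SAP Table 8 follow from

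half-width = t(0.975, n−2) × SD × √(4/n).

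For n=60 and SD=100: 2.0017 × 100 × √(4/60) = 51.68, matching the stated 51.7. All other entries in both tables reproduce to one decimal. The tables count participants with at least one post-baseline S/F ratio, so a participant withdrawn under 7.2.1 normally still counts and the primary half-width is unchanged.

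**5. By-day S/F, with an assumed 1 to 6 of 60 excluded (SD 100)**

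| Excluded | n | Half-width |
|---|---|---|
| 0 | 60 | 51.68 |
| 1 | 59 | 52.14 |
| 3 | 57 | 53.09 |
| 6 | 54 | 54.61 |
| 6, all in one arm | 30 vs 24 | t(0.975, 52) × 100 × √(1/30 + 1/24) = 54.95 |

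**6. One uncaptured death by Day 14.** Scoring the pre-withdrawal trough T instead of 0 raises the mean of a 30-participant arm by T/30. For assumed troughs:

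- T = 90 (SpO2 90% on FiO2 1.00): 90/30 = 3.0
- T = 200: 200/30 = 6.7
- T = 300: 300/30 = 10.0

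**7. Timing limit.** An event starting on Day 11 reaches the 72-hour mark on Day 14 (11 + 3), so onset on Day 11 or later costs little or no primary-window data.

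**The case against.** The strongest reply is that this is a slip of terminology with little effect. The sentence sits under a heading about stopping treatment, and the surrounding text points towards retention. The exception list in SAP 7.3.1 is not exhaustive (it also omits loss to follow-up), so the absence of Grade 3 events from it proves little alone. Exposure is narrow: COVID-attributed non-GI events are exempt, patients with Grade 3–4 GI symptoms are excluded at entry, and earlier studies reported no severe AEs. Once a participant is discharged, the primary trough uses pre-discharge readings anyway. The trial is a descriptive pilot with no power calculation, and Table 4 already contemplates a half-width of 55.7 at n=52.

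The uncaptured death needs a chain of unlikely steps. SAP 5.3.3.3 scores any death by Day 14 as 0 without qualification. Protocol 8.3.1 collects SAEs to 28 days after the last dose. Protocol 7.3 asks withdrawn participants for the follow-up visit assessments, which include the ordinal scale.

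The points about size stand. The death scenario is a remote case, and the Day 42 OSCI score may still be obtained. They do not remove the conflict. The sentence is mandatory as written and Protocol Section 5 permits no waivers, so a site that reads it literally is following the protocol. Protocol 4.4 treats a withdrawn participant as having completed the study, and 8.3.1 does not oblige investigators to seek events after participation ends, so later capture is not assured.

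The other safeguards are also partial. Replacement within one week (7.5) restores numbers but not that participant's outcomes. The MMRM sensitivity analysis (SAP 9.3.1.2) runs only if at least 10% withdraw before Day 14, and it addresses by-day S/F, not the trough.

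**Conclusion.** The concern holds. Protocol 7.2.1 requires study withdrawal for an event less severe than those for which 7.2.2 stops dosing only, and this is at odds with the treatment-policy handling in the SAP. The contradiction is certain; the number of participants affected is unknown and may be small.

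Precision is a minor matter: there is normally no change for the primary endpoint, and at most about 3 points on the by-day half-width (54.61 − 51.68 = 2.93, or 3.27 if all six exclusions fall in one arm), given SD 100 and the assumed 1–6 exclusions. The more important cost is avoidable missing data triggered by an AE: a truncated trough that can only look equal or better, lost daily S/F and OSCI scores, and early censoring. The shift of 3.0 to 10.0 points in an arm mean applies only if a death by Day 14 goes unrecorded, and rests on assumed troughs of 90 to 300. A difference between arms is possible but not shown.

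**What to change.** In both bullets of Protocol 7.2.1, replace the study-withdrawal consequence with permanent discontinuation of study treatment. State that scheduled assessments continue to Day 42, as in 7.2.2 and SAP 7.3.1, unless the participant withdraws consent. The 72-hour pause and the dosing stop rules stay as they are, so participant protection is unchanged.

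The cost is a wording change in two bullets, with IRB approval under Protocol 10.1.1 unless the sponsor considers it non-substantial. The visits and telephone calls to Day 42 already exist, and no SAP table needs to change.

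A separate minor point could go in the same amendment. Protocol 8.2.5 says a positive HIV screening result leads to exclusion or study withdrawal, while 7.2.2 lists a new HIV diagnosis as a dosing stop. The two should agree for a result that arrives after dosing has begun.

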7.2.2 Permanent Cessation of Dosing in an Individual Participant

It may be necessary for a participant to permanently discontinue study treatment. If study drug is definitively discontinued, the participant will be encouraged by the investigator to continue to participate in all scheduled study visits and assessments, so that study data will be collected for the participant per protocol. Every effort should be made to keep participants in the study. Individual treatment stopping rules are:

- “Any CTCAE grade 4 gastrointestinal-related adverse event.”
- “Any non GI-related CTCAE grade 4 adverse event, not attributed to Covid-19 infection.”
- “A new diagnosis of HIV / AIDS”

7.3 Withdrawal from the Study

Participants may withdraw from the study at any time at their own request, or they may be withdrawn at any time at the discretion of the investigator for safety, behavioral, compliance, or administrative reasons. The investigator will also withdraw participant(s) if Evelo terminates the study.

If the participant withdraws consent for disclosure of future information, the sponsor may retain and continue to use any data collected before such a withdrawal of consent.

If a participant withdraws from the study, he/she may request destruction of any samples taken and not tested, and the investigator must document this in the CRF.

Participants who withdraw from the study should complete the assessments for the follow-up visit.

7.4 Lost to Follow Up

A participant will be considered lost to follow-up if he or she has been discharged or transferred to another hospital, and the study site is unable to contact the participant for their telephone visit.

Before a participant is deemed lost to follow-up, the investigator or designee must make every effort to regain contact with the participant by telephone. These contact attempts should be documented in the CRF.

If the participant continues to be unreachable after 3 attempts, he/she will be considered to have withdrawn from the study.

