8.1.4 Telephone call

If patients are discharged, they will be contacted by telephone on days 7, 14, 21 and 42 (+/- 1 day). The purpose of this call is to seek reporting of AEs, remind the participant to continue to fill their daily questionnaire (until symptoms have resolved or Day 42, whichever is sooner), and to offer the opportunity for any study-related questions.

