5.3.3.5 Overall Survival and Intubation and Mechanical Ventilation Free Survival

Overall survival (OS) is defined as the time in days from randomization until death by any cause.

Intubation and mechanical ventilation free survival (IMVFS) is defined as the time in days from randomization until the earliest event of death by any cause or requirement for intubation and/or mechanical ventilation as indicated by the first occurrence of a WHO OSCI score of 6 or above.

Participants who complete the 42-day study period or prematurely withdraw from the study without experiencing the relevant event will be censored on the date of study completion/withdrawal.

Participants who prematurely withdraw from treatment but remain in the study will not be censored and will continue to be followed up until the first occurrence of the relevant event, study completion or withdrawal from the study.

Time to the relevant event will be calculated as:

$$\text{Time to event (days)} = \text{Date of event/censoring} - \text{date of randomization} + 1$$

5.3.3.6 Time to Discharge, Time to SpO2 ≥94% on Room Air and Time to Recovery

Time to discharge is defined as the time in days from randomization until the date of discharge.

Time to SpO2 ≥94% on room air is defined as the time in days from randomization to the first day at which an SpO2 measurement ≥94% on room air is reported after which there were no further requirements for oxygen therapy during the study.

Time to recovery is defined as the time in days from the date of symptom onset until the first day on which a WHO OSCI score of 0 is reported with no further increase above 0 during the study.

Participants who die during the study before the relevant event occurring will be given a status of 'death' which will be considered as a competing risk rather than an event or a censored observation in the analysis.

Participants who are still alive at the end of the 42-day study period or who withdraw prematurely from the study for reasons other than death without experiencing the relevant event will be censored on the date of study completion/withdrawal.

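### Protocol 7.4 turns three failed telephone attempts into study withdrawal with no status check, so a transferred participant too ill to answer can be censored because of the outcome

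*Protocol*

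**What the plan says.** Protocol 7.4 applies to a participant who has been "discharged or transferred to another hospital, and the study site is unable to contact the participant for their telephone visit". Before the label is given, "the investigator or designee must make every effort to regain contact with the participant by telephone", and the attempts must be documented. The section then closes: "If the participant continues to be unreachable after 3 attempts, he/she will be considered to have withdrawn from the study". It sets no spacing between attempts and names no source of information other than the participant.

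The SAP attaches consequences to that status. For overall survival and for intubation and mechanical ventilation free survival (ventilation-free survival below), section 5.3.3.5 says that those who "prematurely withdraw from the study without experiencing the relevant event will be censored on the date of study completion/withdrawal". Table 12 repeats this for any withdrawal: "Participants will be censored at the time of withdrawal from the study". For the WHO OSCI, sections 5.3.3.4 and 9.3.3.1 leave scores missing after a withdrawal of this kind. The one exception is an outpatient whose diary has shown two consecutive days without symptoms and with usual activities resumed, who is given 0 through Day 42. For the primary endpoint, Table 9 says of withdrawal before Day 14: "Trough S/F ratio prior to starting study withdrawal will be used".

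**The concern.** The rule does not separate a participant who will not answer from one who cannot. It names transferred patients explicitly, and a person moved to another hospital and then intubated or sedated is among the least able to take a call. For such a person the event of interest causes the failed contact, the failed contact causes the withdrawal, and the withdrawal causes the censoring. Kaplan-Meier and Cox analyses assume that censoring carries no information about risk given the covariates; here it would.

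The rule also pulls against other parts of the plan. Protocol 7.1 keeps participants admitted to ICU in the study to Day 42 for data collection where practical. SAP 7.3.1 keeps those who stop treatment in the study unless they die, start another experimental treatment or withdraw consent; being unreachable is not on that list. A patient transferred to an ICU elsewhere is retained under those two sections but can be withdrawn under 7.4.

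**Working it through.** The plan gives no expected loss rate or event rate for these endpoints, so there is no figure of its own to reproduce. The check is a reading of linked sections, followed by an illustration on assumed counts.

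1. **When the rule can bite.** Protocol 8.1.4 and note 5 of the Schedule of Activities write the Day 7, 14, 21 and 42 calls for discharged participants. For everyone else the schedule labels only Day 21 and Day 42 as telephone visits. For a patient transferred while still in hospital, the first clear telephone visit is therefore Day 21.

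2. **What triggers it.** Three failed attempts. Because no spacing is set, all three may fall around one visit. Nothing in 7.4 requires asking the receiving hospital, a nominated contact or the record.

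3. **Which endpoints are touched.**
   - Overall survival and ventilation-free survival: censored at withdrawal unless an event is already recorded.
   - OSCI: later scores are missing. The recovery exception does not help a transferred inpatient. The maximum score (SAP 9.3.3.2) uses reported values, so an unreported 6 or 7 lowers it.
   - Primary trough: for a discharged participant Table 9 uses the pre-discharge trough whatever happens later. For a transferred one, Day 21 falls after the Day 1-14 window, and S/F values after transfer are lost only if the site does not obtain them.

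4. **Censoring date.** It is the withdrawal date, not the date last known event-free. With no diary or record in between, the unobserved gap counts as event-free: 21 - 14 = 7 days between the Day 14 and 21 calls, and 42 - 21 = 21 days between the Day 21 and 42 calls.

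5. **Planned sensitivity analyses.** For the two survival endpoints, SAP 9.3.4.2 plans only one, for a newly approved standard-of-care medication. By contrast, SAP 5.3.3.7 and 5.3.3.8 build worst-case variables for oxygen days and pyrexia days after withdrawal.

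6. **Size, with assumed counts.** The arm size is 60/2 = 30 (Protocol 9.1). Assume 6 true ventilation or death events in an arm, on Days 3, 5, 7, 10, 12 and 16. The estimated event probability is 1 - Π(1 - d/r), with d events among r at risk on each event day.
   - All seen: 1 - (29/30)(28/29)(27/28)(26/27)(25/26)(24/25) = 1 - 24/30 = 20.0%.
   - Last one unseen, censored on Day 21: 1 - 25/30 = 16.7%, which is 3.3 points low.
   - Last two unseen, censored on Day 21: 1 - 26/30 = 13.3%, which is 6.7 points low.
   - If the censoring instead preceded every seen event: 5/29 = 17.2% and 4/28 = 14.3%.
   - Counting the lost participants as events: 6/30 = 20.0% again.

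7. **Between arms.** If all the unseen events fell in one arm and there were no true effect, the risk ratio would read 5/6 = 0.83 or 4/6 = 0.67. If they fell equally in both arms, the ratio would stay at 1, both risks would be understated, and the total would drop from 12 events to 10 or 8.

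**The case against.** The strongest reply is that 7.4 is less severe than it looks and that other provisions recover the data.

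- A reader might infer that one missed call ends participation. It does not: every effort and three documented attempts are required. This stands.
- A reader might also infer that a transferred, ventilated patient is lost from Day 7, forfeiting 42 - 7 = 35 days. The Day 7 and 14 calls are written for discharged participants, so that figure can apply only to them. This stands.
- A reader might infer that the primary trough is cut short before deterioration. Step 3 shows that 7.4 itself changes it little. This stands.
- Mortality status, discharge status and the ordinal scale are schedule items taken from the patient record where available. Clinical data are retrieved from the record at Day 42, assessments continue for those still in hospital after Day 14, and 8.3 lets a caregiver or representative report adverse events. An event found by these routes before withdrawal is kept, because the SAP censors only those without one. This stands in part. None of these steps is required before withdrawal is declared, and the documents do not say whether extraction continues afterwards or reaches another hospital's records. Loss of the event is possible, not certain. The follow-up assessments that Protocol 7.3 asks of those who withdraw need a participant who can be reached.
- The study is an unpowered pilot with analyses labelled descriptive, and both survival endpoints are secondary. This stands and limits the severity.

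**Conclusion.** The point holds as a gap in follow-up and in the survival analyses. Section 7.4 states a rule under which inability to answer becomes withdrawal, and the SAP turns that withdrawal into censoring with no sensitivity analysis behind it. The effect falls mainly on overall survival, ventilation-free survival and OSCI.

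On the assumed counts, each unseen event lowers an arm's estimated risk by about 3 points out of 20. The event rate, the event days and the number unseen are assumptions; the documents support none of them. What carries over is that in arms of 30, one or two misclassified events are visible in the result, and the study is meant to inform the size of later ones.

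A reader might go further and infer a bias in favour of EDP1815. The documents do not support that: the same rule applies in both blinded arms, and nothing indicates in which arm more such losses would occur. The change is worth making because it is cheap, not because the trial's main conclusion depends on it.

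**What to change.** **Protocol 7.4**
- State that failed telephone contact is not a withdrawal and that later scheduled contacts are still attempted. Keep withdrawal for those who withdraw or are actively withdrawn.
- For transferred or unreachable participants, obtain vital status and OSCI, and S/F ratio where recorded, from the receiving hospital's record or a nominated contact.
- Assign loss to follow-up only after these routes have failed through Day 42.
- Reconcile 7.4 with 7.1 and with SAP 7.3.1.

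**SAP 5.3.3.5 and 9.3.4**
- Censor at the date last known event-free. This stops unobserved time counting as follow-up, but does not by itself make the censoring uninformative.
- Add a sensitivity analysis for overall survival and ventilation-free survival that counts losses through failed contact as events. It is a pessimistic bound rather than an estimate, and it follows the approach already used for oxygen and pyrexia days.

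**Cost.** One protocol paragraph, a short SAP addition, a few more calls and record requests, and possibly a consent line for records held elsewhere. The consent pages are not among the documents, so the need for that line cannot be checked.
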